### 13.6 Regulatory Reporting

If an event is serious, unexpected, and suspected to be related to the investigational product, the event is considered to be reportable to Health Authorities (HAs) as a Suspected Unexpected Serious Adverse Reaction (SUSAR).

An event is determined to be unexpected if it is not listed in the current Reference Safety Information (e.g., Investigator's Brochure (IB)) or when the specificity or severity of the event is not consistent with the current Reference Safety Information.

Fatal or life-threatening SUSARs must be reported to the required HA(s) within 7 calendar days after the Sponsor's initial receipt of information.

All other SUSARs must be reported to the required HA(s) within 15 calendar days after Sponsor's initial receipt of information.

The Sponsor-Investigator reports all SUSARs to the FDA under the Investigator's IND.

Incyte is responsible for the following:

- Meeting expedited reporting requirements to HAs in their respective territories

- Cross-reporting any SUSAR originating from the IST to the applicable Incyte IND(s)
- Distributing Investigator Notifications to Investigators participating in the applicable Incyte IND(s)

### 13.7 Procedure for Reporting Pregnancy

Data on fetal outcome are collected for regulatory reporting and drug safety evaluation. Follow-up should be conducted for each pregnancy to determine outcome, including spontaneous or voluntary termination, details of the birth, and the presence or absence of any birth defects, congenital abnormalities, or maternal and/or newborn complications.

Within 72 hours of learning of the pregnancy, the investigational site completes the Clinical Trial Pregnancy Form (sections I, II, and question 18 in section III) or equivalent, and e-mails the report to Incyte at [[contact]](mailto:[contact]).

Within 72 hours of learning of the abnormal outcome of the pregnancy (for example, delivery, termination, or miscarriage, abnormal newborn), the investigational site completes the Clinical Trial Pregnancy Form (sections II, III, IV, and V) or equivalent, and e-mails the report to Incyte at [[contact]](mailto:[contact]). Delivery of normal new born will be reported to Incyte in 7 days of learning.

**NOTE:** If a woman has a positive pregnancy test at Baseline, the investigational site completes Clinical Trial Pregnancy Form (sections I, II, and III (question 18)) or equivalent and e-mails the report to Incyte at [[contact]](mailto:[contact]), as per established timelines.

Any SAE occurring during pregnancy must be reported to Incyte as an SAE, in accordance with Section 3 of this Plan.

### 13.8 Additional Reporting Requirements for IND Holders

For Investigator-Sponsored IND Studies, some additional reporting requirements for the FDA apply in accordance with the guidance set forth in 21 CFR § 312.32. Events meeting the following criteria need to be submitted to the Food and Drug Administration (FDA) as expedited IND Safety Reports according to the following guidance and timelines:

#### 7 Calendar Day Telephone or Fax Report:

The Investigator is required to notify the FDA of any fatal or life-threatening adverse event that is unexpected and assessed by the investigator to be possibly related to the use of therapy. An unexpected adverse event is one that is not already described in the therapy Investigator Brochure. Such reports are to be telephoned or faxed to the FDA and Incyte within 7 calendar days of first learning of the event.

## 15 Calendar Day Written Report

The Investigator is also required to notify the FDA and all participating investigators, in a written IND Safety Report, of any serious, unexpected AE that is considered reasonably or possibly related to the use of THERAPY. An unexpected adverse event is one that is not already described in the THERAPY investigator brochure.

Written IND Safety reports should include an Analysis of Similar Events in accordance with regulation 21 CFR § 312.32. All safety reports previously filed by the investigator with the IND concerning similar events should be analyzed and the significance of the new report in light of the previous, similar reports commented on.

Written IND safety reports with Analysis of Similar Events are to be submitted to the FDA, Incyte, and all participating investigators within 15 calendar days of first learning of the event. The FDA prefers these reports on a MedWatch 3500 form, but alternative formats are acceptable (e.g., summary letter).

Under requirements of 21 CFR 312.23, the completed MedWatch form and FDA Form 1571 must be sent to the FDA..

FDA fax number for IND Safety Reports:

[name]

All written IND Safety Reports submitted to the FDA by the Investigator must also be faxed to UC Davis IRB per institutional policies:

IRB Administration  
[name]  
[name]  
[name]  
[contact]  
[contact]

## 13.9 Study Close-Out

Any study report submitted to the FDA by the Sponsor-Investigator should be copied to Incyte. This includes all IND annual reports and the Clinical Study Report (final study report). Additionally, any literature articles that are a result of the study should be sent to Incyte.

## **14. ETHICAL CONSIDERATIONS AND ADMINISTRATIVE PROCEDURES**

### **14.1 Ethics and Good Clinical Practice**

This study must be carried out in compliance with the protocol and Good Clinical Practice, as described in:

1. ICH Harmonized Tripartite Guidelines for Good Clinical Practice 1996.
2. Directive 91/507/EEC, The Rules Governing Medicinal Products in the European Community.
3. US 21 Code of Federal Regulations dealing with clinical studies (including parts 50 and 56 concerning informed consent and IRB regulations).
4. Declaration of Helsinki, concerning medical research in humans (Recommendations Guiding Physicians in Biomedical Research Involving Human Subjects, Helsinki 1964, amended Tokyo 1975, Venice 1983, Hong Kong 1989, Somerset West 1996).

The investigator agrees, when signing the protocol, to adhere to the instructions and procedures described in it and thereby to adhere to the principles of Good Clinical Practice that it conforms to.

### **14.2 Institutional Review Board/Independent Ethics Committee**

Before implementing this study, the protocol, the proposed informed consent form and other information to subjects, must be reviewed by a properly constituted Institutional Review Board/Independent Ethics Committee (IRB/IEC/REB). A signed and dated statement that the protocol and informed consent have been approved by the IRB/IEC/REB must be given to Incyte before study initiation. The name and occupation of the chairman and the members of the IRB/IEC/REB must be supplied to Incyte. Any amendments to the protocol, other than administrative ones, must be approved by this committee.

### **14.3 Study Documentation**

The required documents include, but are not limited to the following: IRB approvals (i.e., protocol, consent form, amendments, patient brochures and recruitment material, etc.), IRB membership rosters, summary of unanticipated problems or protocol deviations, and documentation of expertise of the investigators.

### **14.4 Informed Consent**

The investigator must explain to each subject (or legally authorized representative) the nature of the study, its purpose, the procedures involved, the expected duration, the potential risks and benefits involved and any discomfort it may entail. Each subject must be informed that participation in the study is voluntary and that he/she may withdraw from the study at any time

and that withdrawal of consent will not affect his/her subsequent medical treatment or relationship with the treating physician.

This informed consent should be given by means of a standard written statement, written in non-technical language. The subject should read and consider the statement before signing and dating it, and should be given a copy of the signed document. If the subject cannot read or sign the documents, oral presentation may be made or signature given by the subject's legally appointed representative, if witnessed by a person not involved in the study, mentioning that the patient could not read or sign the documents. No patient can enter the study before his/her informed consent has been obtained.

The informed consent form is considered to be part of the protocol, and must be submitted by the investigator with it for IRB/IEC/REB approval.

Fertile men and women of child bearing potential should be informed that taking the study medication may involve unknown risks to the fetus if pregnancy were to occur during the study and agree that in order to participate in the study they must adhere to the contraception requirement for the duration of the study.

Acceptable methods of birth control for men and women are the following:

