##### 4.1 Inclusion Criteria

1. Adults  $\geq 18$  years of age with histologically proven solid malignancy, high-grade lymphoma or low-grade lymphoma.
2. Patients with incurable, advanced or metastatic disease refractory to at least one previous line of therapy.
3. ECOG (Eastern Cooperative Oncology Group) performance status score of 0 – 2 (Appendix 1).
4. Presence of a candidate treatment lesion (subcutaneous, nodal, or visceral) accessible and safe for radiotherapy and serial intralesional injections as specified by the protocol.
5. Presence of at least one target lesion (distinct from treatment lesion and outside of treatment lesion radiation field) evaluable for response by irRECIST.
6. 14 day wash-out period from any previous chemotherapy, targeted therapy or radiotherapy, 21 day washout period from previous immunotherapy.
7. Life expectancy  $\geq 6$  months.
8. Adequate hematologic and end organ function, defined by the following laboratory results obtained within 14 days of the first study treatment:
  - o ANC  $> 1500$  cells/uL; WBC count  $> 2500$ /uL; Platelet count  $> 50,000$ /uL; Hemoglobin  $> 9$  g/dL
9. Liver function tests meeting one of the following criteria:
  - a. AST and ALT  $< 2.5$  x ULN with alkaline phosphatase  $\leq 2.5$  x ULN OR

- b. AST and ALT  $\leq 1.5 \times$  ULN, with alkaline phosphatase  $> 2.5 \times$  ULN
  - c. Serum bilirubin  $\leq 1.0 \times$  ULN. Direct bili  $\leq 40\%$  if total bili  $>$  ULN in patients with Gilbert's syndrome.
10. INR and aPTT  $< 1.5 \times$  ULN.
  11. Serum Cr  $\leq 1.5 \times$  ULN or CrCl  $\geq 50$  ml/min.
  12. No active auto-immune disease and not on therapy for auto-immune disease. Patients with a history of autoimmune-related hypothyroidism on a stable dose of thyroid replacement hormone are eligible. Patients who have adrenal insufficiency and hypophysitis from prior immunotherapy if they are on stable medical replacement doses are eligible.
  13. No other active malignancy.
  14. Patients with controlled Type 1 diabetes mellitus on a stable insulin regimen are eligible.
  15. For female patients of childbearing potential and male patients with partners of childbearing potential agreement (by patient and/or partner) to use highly effective form(s) of contraception (i.e., one that results in a low failure rate [ $<1\%$  per year] when used consistently and correctly) and to continue its use for 6 months after trial completion.
  16. Signed informed consent.

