**7. CONCOMITANT AND EXCLUDED THERAPIES**

**7.1 Concomitant Therapy**

The patient must be told to notify the investigational site about any new medications he/she takes after the start of the study drug. All medications (other than study drug) and significant non-drug therapies (including blood transfusions) administered during the study should be recorded.

Concomitant therapy includes any prescription medications or over-the-counter preparations used by a patient between the 7 days preceding the screening evaluation and the treatment discontinuation visit.

Patients who experience infusion-associated symptoms may be treated symptomatically with antipyretics (ibuprofen preferred), diphenhydramine, and/or cimetidine or another H2 receptor antagonist, as per standard practice. Serious infusion-associated events manifested by dyspnea, hypotension, wheezing, bronchospasm, tachycardia, reduced oxygen saturation, or respiratory distress should be managed with supportive therapies as clinically indicated (e.g. supplemental oxygen and  $\beta_2$ -adrenergic agonists).

Systemic corticosteroids and TNF $\alpha$  inhibitors may attenuate potential beneficial immunologic effects of treatment but may be administered at the discretion of the treating physician. If feasible, alternatives to corticosteroids should be considered. Premedication may be administered for Cycles  $\geq$  2 at the discretion of the treating physician. The use of inhaled

corticosteroids and mineralocorticoids (e.g., fludrocortisone) for patients with orthostatic hypotension or adrenocortical insufficiency is allowed. Megastrol administered as appetite stimulant is acceptable while the patient is enrolled in the study.

Patients who use oral contraceptives, hormone-replacement therapy, prophylactic or therapeutic anticoagulation therapy (such as low-molecular-weight heparin or warfarin at a stable dose level), or other allowed maintenance therapy should continue their use. Males and females of reproductive potential should use highly effective means of contraception.

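### Section 14.4 states a shorter and looser contraception rule than inclusion criterion 15: it omits the 6 months after trial completion and accepts a second tier of methods not classed as highly effective

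*Combined protocol and SAP*

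**What the plan says.** Three parts of the combined protocol and SAP deal with contraception.

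- **Section 4.1, criterion 15.** Entry requires "agreement (by patient and/or partner) to use highly effective form(s) of contraception". The criterion explains the term as "one that results in a low failure rate", with the threshold set below 1% per year. The patient must also agree "to continue its use for 6 months after trial completion".
- **Section 7.1.** "Males and females of reproductive potential should use highly effective means of contraception". No duration or failure rate is given.
- **Section 14.4.** Fertile men and women of childbearing potential are to be told that "taking the study medication may involve unknown risks to the fetus" should pregnancy occur while they are on study. To take part they must agree that "they must adhere to the contraception requirement for the duration of the study". The section continues "Acceptable methods of birth control for men and women are the following" and gives two accepted tiers. *Highly effective methods* holds vasectomy, true abstinence, and hormonal birth control for a male patient's partner. *Effective methods* holds an intrauterine device or system, a condom with spermicide, and an occlusive cap with spermicide. A third list rules out only periodic abstinence and withdrawal.

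Section 14.4 also states: "The informed consent form is considered to be part of the protocol".

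**The concern.** Section 14.4 governs the consent discussion, so it is the natural source for an investigator explaining what is being asked. Followed as written, it leads to counselling that differs from criterion 15 in two ways: the obligation ends with the study, and methods the protocol does not itself class as highly effective are acceptable on their own. A patient could then act in good faith on that advice and depart from the agreement given at entry.

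Contraception is also the main continuing safeguard in this trial. The study calendar (Section 9.1) schedules a serum pregnancy test at screening only, while Section 3 allows epacadostat to continue for 12 months and, in some patients, longer. The rule should therefore read the same wherever it appears.

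**Working it through.** No statistical calculation applies, and the plan gives no figure to reproduce. The check is a side-by-side reading.

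| Element | Criterion 15 (4.1) | Section 7.1 | Section 14.4 |
|---|---|---|---|
| Standard | Highly effective, failure below 1% per year | Highly effective, no rate | Two tiers, both introduced as acceptable, no rate |
| Period after the trial | 6 months | Not stated | None stated |
| Combining methods | Not stated | Not stated | Not required |

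**Duration.** At face value the gap is 6 − 0 = 6 months. This assumes that the study in 14.4 and the trial in criterion 15 end on the same date, and neither end date is defined. If the end meant in 14.4 falls *d* months after trial completion, the gap is 6 − *d*, and it closes only when *d* is 6 or more. Section 3 places the 3-monthly follow-up after study completion, which fits *d* near 0. Section 15.2 has every patient monitored for at least 12 months, so a reader who counts that monitoring as part of the study could reach a larger *d* for a patient who stops treatment early. The 6 months is the plain reading, not an established quantity.

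**Method.** The conflict rests on the protocol's own headings. Criterion 15 asks for highly effective methods, and 14.4 separates those from a tier called merely effective and accepts both. The documents give no failure rate for the intrauterine device or system, the condom with spermicide or the cap with spermicide. They therefore do not show whether any of the three meets the 1% standard, and the size of this gap cannot be stated.

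**Options for female patients.** The highly effective list has three entries. The hormonal entry is restricted to the partners of male patients, which leaves 3 − 1 = 2 for women: a vasectomised sole partner or true abstinence. Section 7.1 tells patients on oral contraceptives to continue them, yet a female patient's own hormonal method appears in neither tier of 14.4. Simply deleting the second tier would leave most of the problem for women unsolved.

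**The case against.** The strongest reply is that criterion 15 already governs. It is a condition of entry, Appendix 2 (item E) bars registration of anyone who does not meet all requirements, Section 7.1 repeats the highly effective standard, and 14.4 itself says that patients unlikely to comply reliably should not be entered. The definite article in 14.4's reference to the contraception requirement can be read as pointing back to criterion 15. All of this stands, and it limits the practical effect. It does not reconcile the texts: even on that reading, 14.4 attaches its own period and its own list of acceptable methods to the requirement.

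Three stronger readings are tempting, and the documents do not support them.

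- **That stopping contraception at study end exposes a fetus to shown harm.** The fetal-risk sentence in 14.4 concerns pregnancy during the study. The epacadostat half-life is given as 2.9 hours (Section 2.4.4.1), SD-101 dosing ends on day 29 and radiotherapy is confined to week 1 (Table 2). Section 2.4.3.1 reports fetal allograft rejection in mice with a different inhibitor of the same pathway, which is a reason for caution and not an estimate of post-study risk. The short exposure does not prove safety either.
- **That patients were given the wrong instruction.** Patients receive a written consent statement, which was not among the pages available. It may already state the 6 months.
- **That the second-tier methods fail the 1% standard.** With no failure rates in the documents, this cannot be concluded for any of the three.

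**Conclusion.** Section 14.4 is wrong as written because it conflicts with criterion 15 on a safety rule, and no other section repairs it. The duration conflict is the firmer half: 6 months against none, on the assumption that study and trial end together. The method conflict is real at the level of the protocol's own labels, but it cannot be sized.

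Severity is low. Criterion 15 remains in force at entry, the content of the consent form is unknown, and a reader who inferred demonstrated harm to participants would be going beyond the documents. Sample size, endpoints and analysis are untouched.

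**What to change.** Make criterion 15 the governing rule and bring Section 14.4 into line with it.

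1. Extend the period in 14.4 by adding, after the reference to the study's duration, *and for 6 months after trial completion*.
2. State in 14.4 that only methods, or named combinations of methods, meeting the criterion 15 standard of less than 1% failure per year are acceptable.
3. Re-sort the list on that single test, applied equally to all three entries now in the second tier. Failure rates will have to come from a source outside the protocol, which the amendment should cite. Include options for female patients beyond the two they now have, and settle where their own hormonal contraception stands, given Section 7.1.
4. Check that the consent form carries the same period and the same list.

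The cost is a wording amendment, which under Section 14.6 needs ethics committee approval and the supporting company's agreement, plus a review of the consent form. The downside is that some listed methods may no longer be accepted alone, but criterion 15 already implies this.

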#### Highly effective methods

- Male sterilization (vasectomy). For female patients, the vasectomized male partner should be the only partner
- True abstinence, if this is your preferred and usual lifestyle
- Hormonal birth control for male patient's partner

#### Effective methods

- Placement of intrauterine device or intrauterine system
- Condom with spermicidal foam/gel/film/cream/suppository
- Occlusive cap (diaphragm or cervical/vault caps) with spermicidal foam/gel/film/cream/suppository

#### Unacceptable methods

- Abstinence at certain times of the cycle only, such as during the days of ovulation, after ovulation (based on symptoms or temperature)
- Pre-ejaculatory withdrawal

If there is any question that the patient will not reliably comply, they should not be entered in the study.

In accordance with UCD OCR policy an original signed and dated participant Informed Consent document will reside in a secured location at participating institutions. Copies of the signed and dated Informed Consent document will be provided to the study participant and a copy will be stored in the patient's electronic medical record at the participating institution.

#### **14.5 Discontinuation of Study Support**

Incyte reserves the right to discontinue support for any study under the conditions specified in the clinical trial agreement.

#### **14.6 Amendments to the Protocol**

Any change or addition to this protocol requires a written protocol amendment that must be approved by Incyte and the investigator before implementation. Any protocol amendment requires approval by the IRB/IEC/REB. A copy of the written approval of the IRB/IEC/REB, must be sent to Incyte.

#### **14.7 Patient Confidentiality**

In order to maintain patient privacy, all study reports and communications will identify the patient by initials and the assigned patient number. Data capture records and drug accountability records will be stored in secure cabinets in the department of radiation oncology, UC Davis or at the participating institutions. Medical records of patients will be maintained in strict confidence according to legal requirements. The investigator will grant monitor(s) and auditor(s) from Incyte or its designees and regulatory authority(ies) access to the patient's original medical records for verification of data gathered on the data capture records and to audit the data collection process. The patient's confidentiality will be maintained and will not be made publicly available to the extent permitted by the applicable laws and regulations.

#### **14.8 Protocol Deviations**

All protocol deviations will be reported in accordance with UCD IRB Administration and UCD Cancer Center OCR policies.

